Study Protocol including Statistical Analysis Plan

Official Study Title: Extreme Exercise and Energy Expenditure (4E) Study

NCT Number: N/A

Document Date: June 13, 2018

BACKGROUND

Although there is robust evidence that a physically active lifestyle including regular leisure time physical activity and exercise (>150 min per week of moderate to vigorous exercise per week) is associated with a reduced mortality risk and improved cardiometabolic health (1), some scientists have promoted the notion (which has certainly been taken up the lay press) that if one wants to lose weight, focus should be placed on caloric restriction rather than on exercise (2, 3). Several academic debates have been held on this issue (4, 5) which have left some health professionals and the public confused and perplexed (6).

Our research group has been active in this area on several fronts. First, we have pioneered the notion that in cardiovascular and "metabolic" medicine, the health risk of overweight and obesity was not appropriately assessed by an index based on body weight (body mass index, which is expressed in kg/m2) (7-9). For instance, using imaging technology (computed tomography), we were among the first, more than 30 years ago, to begin to extensively study regional body fat distribution, showing that excess visceral adipose tissue accumulation was more closely related to an atherogenic and diabetogenic cardiometabolic risk profile than excess body weight or total body fat (7). As sedentary individuals with a diet of poor nutritional value (rich in processed fat and added sugar promoting preferential visceral fat deposition) are also often characterized by a lower muscle mass and by high levels of abdominal visceral fat (9), several lifestyle intervention studies that we and others (10, 11) have conducted in viscerally obese sedentary men have shown that with regular exercise, one could lose visceral adipose tissue while gaining muscle mass, which would lead to trivial or sometimes no changes in body weight. Thus, if body composition is altered by an energy deficit produced by regular exercise, we have proposed that weight loss may sometime be misleading as an outcome as it may not always reflect favorable changes in body composition (muscle mass increasing) and in visceral adiposity and levels of ectopic fat (decreasing) (12). On that basis, we have proposed that changes in waist circumference could be more useful than body weight loss in the evaluation of the benefits of a lifestyle modification program involving regular endurance exercise such as brisk walking, jogging, or biking (12). For instance, we have previously reported that waist circumference was rather sensitive to lifestyle changes involving regular physical activity/exercise (10). Accordingly, lifestyle intervention studies have shown that a reduction of 4 cm in waist girth was predictive of a 58% reduction in the risk of developing type 2 diabetes among individuals who were initially characterized by abdominal obesity and glucose intolerance (13, 14).

Thus, there is a need to propose a paradigm shift among health professionals to evaluate the impact of lifestyle intervention programs involving physical activity/exercise in high-risk overweight obese individuals with visceral obesity: Weight loss is no longer the optimal or most clinically relevant outcome – losses of visceral adiposity and ectopic fat may be more relevant clinically.

In 2015, a member of our team was asked to write an editorial (15) on a spectacular study which provided very relevant data to the debate about diet vs. exercise and weight loss. In that impressive exercise study, recreational middle-aged cyclists were required to bike 2,700 km over 14 days and asked to try to match their energy intake to their very large energy expenditure, the objective being not to lose weight over the course of the intervention. Thus, the daily exercise "prescription" was huge as the authors wanted to

test the ability of these elderly and fit recreational cyclists to match their energy intake to their energy expenditure. The most striking and important finding of this unusual study (16) is that despite the huge energy expenditure associated with the 2,700 km bike expedition, participants did not lose weight. However, such lack of change in body weight was completely misleading in terms of energy balance and changes in body composition. Indeed, the cyclists lost 2.2 kg of body fat while gaining 2.5 kg of fat-free mass, a remarkable finding considering that such changes were observed over a period of only two weeks.

Results of this study provide additional evidence that body weight is a poor outcome to assess the effect of a physical activity/exercise program. In our previously published exercise training studies, a common observation has been the disconnect between changes in body weight and changes in body composition, the latter being sometime observed even in the absence of weight loss (10). As weight poorly tracks changes in body composition induced by exercise, no wonder why exercise is indeed perceived as not being helpful to lose weight by some health professionals. We propose that body weight is a misleading outcome when comes the time to evaluate the clinical benefits of exercise in individuals with overweight/obese (9).

One remaining and clinically important issue remains to be addressed regarding the effects of a large volume of exercise not inducing weight loss: to what extent substantial changes in visceral/ectopic fat could have been observed had imaging data been available? In addition, it would have been interesting for the 2,700 km bike intervention study to report changes in waist circumference, this metric being more sensitive to regular exercise than body weight (12). In our previous intervention studies, it has been our experience to find participants losing quite a bit of visceral fat and dropping their waistline by several centimeters, while not losing any body weight.

Thus, on the basis of the above observations, we put forward the hypotheses that:

1- a very large volume of exercise (1,144 km of bicycle performed for 7 consecutive days) will induce major changes in body composition and in levels of visceral adipose tissue/ectopic fat in a sample of middle-aged recreational cyclists who will be asked to match their energy intake to their very large energy expenditure during the course of the one-week extreme exercise intervention. Thus, in a study where, by design, no weight loss is planned nor wanted, we expect to see major changes in body composition (slight increase in muscle mass and substantial reductions in the size of visceral adipose tissue and ectopic fat depots);

2- changes in levels of visceral adipose tissue and ectopic fat will be better reflected by changes in waist circumference – which should decrease in the absence of body weight loss.

We recognize that this is an extreme exercise prescription that has little relevance to public health. However, results of this study will be very important in shedding light on the importance of shifting our attention from body weight loss to other, more clinically relevant fat depots. Thus, the purpose of the study is to provide evidence, through an extreme exercise prescription, that weight loss is not the appropriate outcome to evaluate the effects of exercise on visceral adiposity and ectopic fat depots (e.g. liver fat and epi/pericardial fat) which will likely be mobilized to a very significant extent in only one week.

Research Protocol

A sample of eleven recreational middle-aged male cyclists (aged 50 to 66 years) able to perform such a large volume of exercise over a period of one week and asymptomatic for CVD will be recruited. The cyclists will be relatively fit with previous participation in demanding recreational cycling activities but not retired competitive athletes. From their age, we expect them to have subclinical levels of visceral adipose tissue/ectopic fat (these depots increase in size with age).

For this study, participants will be asked to partake in several evaluations: fasting plasma lipoprotein-lipid profile and inflammation markers, glycated hemoglobin, cardiorespiratory fitness, submaximal exercise test including measurement of energy expenditure, resting and exercise blood pressure and heart rate (HR), evaluation of regional adiposity, liver fat content, epi/pericardial fat, nutritional quality, and level of physical activity. After baseline evaluations, participants will be asked to alternately bike 208 km and 104 km per day on a pre-specified course for seven consecutive days. They will be accompanied during each of the seven bike rides by research professionals in a recreational vehicle. Participants' weight, body composition and waist circumference will be measured under standardized conditions in the morning after an overnight fast and after the exercise. Their HR will be continuously monitored, and participants will wear accelerometers to estimate their daily exercise-related energy expenditure. Foods and fluids will be provided to participants and recorded. Again, from the expected large energy expenditure predicted with HR-EE equations (between 6,000 and 7,000 kcal per day), participants will be asked to eat at least a pre-specified number of calories to be adjusted on the daily basis during the week depending upon subjects evolving body weight recorded every morning in standardized conditions. At the end of the 1,144 km/7-day bike ride, baseline evaluations will be repeated with the exception of the maximal exercise treadmill test, nutritional quality, and level of physical activity. To facilitate the conduct of the protocol, the eleven participants will be evaluated and followed in two distinct groups.

METHODS

A comprehensive set of body fat distribution/ectopic fat variables will be measured on all participants as well as lipids and apolipoproteins, cardiorespiratory fitness, submaximal exercise test with HR and energy expenditure measured by indirect calorimetry, energy expenditure and energy intake evaluation. Questionnaire on nutritional quality and physical activity level will also be performed.

Resting Blood Pressure and Electrocardiogram (ECG)

Blood pressure measurements will be obtained on all subjects by the same nurse using a sphygmomanometer and a stethoscope as previously described (17). Resting blood pressure will be recorded in a supine position after a 15-minute rest. A resting 12-lead ECG will also be performed.

Anthropometry and Body Composition

Height, body weight and waist circumference (18) will be measured using standardized and previously described procedures. The measurement of body composition will be assessed using a bio-impedance device, the InBody 570 (InBody Co., South Korea), which provides an analysis of the body per compartment (arms, trunk, and legs). This exam is designed to measure body water which in turn allows to measure the lean mass and body fat. Bio-impedance will be performed at pre- and post-evaluations as well as every morning prior to the 7-day bike rides.

Fasting Plasma Lipoprotein-Lipid and Apolipoproteins Profiles

Samples are collected in EDTA tubes in the morning after a 12-hour fast while the participants are in a supine position. Cholesterol and triglyceride levels are determined in plasma using automated techniques (20, 21). Apolipoprotein (apo) A1 and B levels were measured on a Dimension Vista 500 System (Siemens Healthineers, Germany) by luminescent oxygen channeling assay on previously frozen plasma samples (-80°C) according to the manufacturer's instructions.

Abdominal Subcutaneous and Visceral Adipose Tissue

All imaging will be performed on a Magnetic Resonance Imaging (MRI) 3T system (Ingenia; Philips Healthcare, software version R5.1.9, Netherlands) using the integrated two-channel body coil for excitation and a 28-channel body array surface coil for signal reception. Axial sequence will cover the abdominal region from L2 to S1. Analyses will be performed at the level of L4-L5 intervertebral disc.

Measurement of Liver Fat

Proton Magnetic Resonance Spectroscopy (MRS) will be performed to determine liver fat content (22).

Measurement of Epicardial and Pericardial Fat

Levels of epicardial and pericardial fat are both related to features of the metabolic syndrome (23-25) and visceral adiposity (25). We therefore intend to measure epicardial (covering the epicardium within the pericardium) and pericardial (outside the pericardium) fat depots by MRI (26). Epicardial and pericardial fat is routinely measured in the non-invasive cardiovascular imaging laboratory at the research center.

Maximal Exercise Test (ETT)

To assess cardiorespiratory fitness (maximal oxygen consumption, VO2 max), all subjects will perform the same symptom-limited maximal exercise test on an Excalibur Sport cycle ergometer (Lode B.V., Netherlands) linked to a Cardio2 Ultima gas analyzer system (MGC Diagnostics, Minnesota, MI, USA). The incremental protocol consists of 3-min steps with increases in the workload of 30 or 35 watts per step. Cardiologists blinded as to LV diastolic status will supervise all exercise tests. Blood pressure will be recorded with an automatic sphygmomanometer and HR will be recorded continuously during exercise. Raw data and average 12-lead ECG will monitor cardiac status every 30 seconds during the exercise test as described (27).

Submaximal Exercise Test (to determine energy expenditure)

The energy expenditure will be estimated using the HR-VO2 relationship. VO2 will be estimated by referring to regression lines of HR on VO2 obtained during the measurement of resting metabolic rate and the energy cost of submaximal activities such as sitting, standing, slow walking, fast walking and cycling at various HRs. Measurements of VO2 during these activities will be performed using indirect calorimetry. The calculation of energy expenditure will be made after stabilization of VO2 and CO2 output, usually during the last 2-3 min of each activity as previously described (28).

Lifestyle Habits Measurements

Accelerometry (Acti-Graph, Pensacola, FL, USA) recording will be used to average the daily energy expenditure at baseline. Sleep time and numbers of steps will also be provided by the accelerometer. Accelerometer will be used to record 24-hour HR during the 7-day bike ride. HR will be used to extrapolate energy expenditure.

The quality of diet will be evaluated using the validated Dietary Screening Tool (DST) for the assessment of a nutritional quality score which can vary from 0 to 100 (29). Dietary habits will be monitored using a validated quantitative web-based food frequency questionnaire. During the 7-day bike ride, food and liquid intakes will be detailed, weighed, and recorded.

Finally, all the methodology proposed in the present protocol is well established and currently used by the team of investigators. We have all the facilities and equipment to conduct the research project as proposed.

STATISTICAL ANALYSES

Data will be expressed as mean \pm SD. The analysis of the main variables will be the differences in changes in visceral adipose tissue and ectopic fat as well as cardiometabolic risk markers to document changes following the extreme exercise week. A paired t-test will be used with a significance level with a *P* value below 0.05.

REFERENCES

- 2. Luke A and Cooper RS. Physical activity does not influence obesity risk: time to clarify the public health message. *Int J Epidemiol*. 2013;42:1831-6.
- 3. Malhotra A, Noakes T and Phinney S. It is time to bust the myth of physical inactivity and obesity: you cannot outrun a bad diet. *Br J Sports Med*. 2015;49:967-8.
- 4. Blair SN, Archer E and Hand GA. Commentary: Luke and Cooper are wrong: physical activity has a crucial role in weight management and determinants of obesity. *Int J Epidemiol*. 2013;42:1836-8.
- 5. Blair SN. Physical inactivity and obesity is not a myth: [name] comments on [name] editorial. *Br J Sports Med*. 2015;49:968-9.

- 6. Lowery M. Why exercising for weight loss just doesn't work *The Telegraph*. http://www.telegraph.co.uk/health-fitness/body/exercising-weight-loss-just-doesnt-work/. Accessed September 1, 2017.

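### Raw plasma concentrations of lipids, apolipoproteins and inflammation markers are compared before and after the ride with no plasma-volume index, so a fluid shift could account for part of a change in any one of them

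*Combined protocol and SAP*

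**What the plan says.** The document is a combined protocol and SAP. Its Research Protocol section describes one group: "A sample of eleven recreational middle-aged male cyclists (aged 50 to 66 years". The baseline blood work there covers "fasting plasma lipoprotein-lipid profile and inflammation markers, glycated hemoglobin, cardiorespiratory fitness". After the ride, "At the end of the 1,144 km/7-day bike ride, baseline evaluations will be repeated with the exception of the maximal exercise treadmill test"; the exceptions do not include the blood tests. The interval from the last ride to the post-ride draw is not given.

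The Methods section on lipoproteins and apolipoproteins reports levels in plasma: "Cholesterol and triglyceride levels are determined in plasma using automated techniques (20, 21". Apo A1 and apo B are also reported as plasma levels. Sampling conditions are fixed: "Samples are collected in EDTA tubes in the morning after a 12-hour fast while the participants are in a supine position".

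Statistical Analyses places the risk markers among the main variables: "as well as cardiometabolic risk markers to document changes following the extreme exercise week". The method is one sentence: "A paired t-test will be used with a significance level with a *P* value below 0.05". No haematocrit, haemoglobin concentration or other plasma-volume index is listed, and no correction, ratio or sensitivity analysis is stated. Bio-impedance body water is measured before, after and on ride mornings, but it is used for lean and fat mass and is not linked to the blood results.

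**The concern.** A plasma concentration is circulating mass divided by plasma volume. The exposure is seven days of riding totalling 1,144 km, with expected expenditure of 6,000 to 7,000 kcal a day and fluids provided, so a change in fluid compartments over the week is foreseeable. If plasma volume rises, every concentration falls with no change in mass; if it contracts, every concentration rises. A paired test on raw concentrations responds to both causes alike, and nothing planned separates them. What is at stake is how a significant change is read: as altered lipoprotein metabolism or inflammation, or partly as altered dilution.

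**Working it through.** **Inputs from the documents.** n = 11, one group, paired t-test, significance level 0.05. Sidedness is not stated; I take it as two-sided. The plan gives no SD, effect size or power, so there is no figure of its own to reproduce.

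**Assumed inputs.** The fractional plasma-volume change x, and the SD of the within-man percentage change. Neither is in the documents, so ranges are shown. Changes are expressed in relative units, with the same x for every man in the table.

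**Step 1, dilution.** With circulating mass unchanged, the relative change in concentration is 1/(1+x) − 1. For x = +10% this is 1/1.10 − 1 = −9.1%. For x = −5% it is 1/0.95 − 1 = +5.3%.

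**Step 2, what the test picks up.** With 10 degrees of freedom the critical t is 2.228. A mean shift reaches it at 2.228/√11 = 0.672 SD. Rejection with 80% probability needs 0.938 SD.

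**Step 3, rejection probability.** Use the noncentral t with 10 degrees of freedom and noncentrality (|concentration change| / SD) × √11. With no shift this returns 0.050, as it should. Worked case: x = +10% and SD 10% give 0.0909/0.10 × 3.317 = 3.02, and rejection probability 0.78.

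| Assumed volume change | Concentration change | SD 8% | SD 10% | SD 15% | SD 20% |
|---|---|---|---|---|---|
| +5% | −4.8% | 0.43 | 0.30 | 0.16 | 0.11 |
| +10% | −9.1% | 0.92 | 0.78 | 0.44 | 0.28 |
| +15% | −13.0% | 1.00 | 0.97 | 0.74 | 0.50 |
| −5% | +5.3% | 0.51 | 0.35 | 0.18 | 0.12 |

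**Step 4, ratios.** Under uniform dilution, [apo B/(1+x)] / [apo A1/(1+x)] = apo B/apo A1, so x drops out. HbA1c is a fraction and cancels in the same way.

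**Step 5, correction.** This was simulated with 40,000 replicates and no change in mass. Mean expansion was 10% or 15%, between-man SD 4%, error in the measured volume change 3%, and SD of change 8% to 15%. Uncorrected, the test rejected in 0.48 to 0.91 of replicates at 10% and in 0.82 to 1.00 at 15%. After multiplying each post-ride value by (1 + measured volume change), it rejected in 0.049 to 0.051. All these inputs are assumptions.

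**The case against.** The strongest case against runs as follows.

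- **The shift is not shown.** Its size and direction, and the timing of the draw, are absent from the documents. This stands. A reader might infer that expansion is the expected case, but fluids are only said to be provided, weighed and recorded, and contraction is equally open.
- **The rates depend on the SD.** This also stands. At an SD of 20% a 5% shift gives 0.11 or 0.12, not far above 0.05. Different analytes may well have different SDs.
- **Sampling is standardised.** Morning, fasted, supine draws limit posture and meal effects. They do not remove a difference in plasma volume between the start and end of the week. Body water offers descriptive evidence on hydration, but it is not plasma volume.
- **A concentration change is real.** Correct: the test would be right about concentration. The error arises only when the change is read as one in circulating mass or metabolism.
- **The aims lie elsewhere.** Both hypotheses concern body composition, visceral and ectopic fat, and waist circumference. The MRI and MRS outcomes are not exposed to dilution. The risk markers are nevertheless among the main tested variables.

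Two stronger readings are tempting. One is that dilution could by itself produce a uniformly favourable risk profile. It could not: uniform dilution lowers apo A1 by the same percentage as apo B, which is a mixed picture, and analytes moving in opposite directions cannot be uniform dilution alone. The other is that the lack of a control group causes the problem. A non-riding control would not share a shift caused by riding, so adding one would not remove it.

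**Conclusion.** The point holds as a limit on interpretation. The plan tests raw concentrations after an exposure likely to disturb fluid balance and has no means of telling how much of a change in any single concentration is fluid shift. Over the assumed ranges, a 10% expansion gives a significant result with probability 0.28 to 0.92 with no change in circulating mass; a 5% shift gives 0.11 to 0.43 for expansion and 0.12 to 0.51 for contraction. These figures rest on the assumed shift and SD, a two-sided test and n = 11. They show what could happen, not that bias occurred.

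The scope is the lipid, apolipoprotein and inflammation-marker concentrations. This reads the unlisted risk markers in Statistical Analyses as including all three, and the inflammation markers, whose assay Methods does not describe, as plasma concentrations. The imaging outcomes and HbA1c are outside it.

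**What to change.** In Statistical Analyses:

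1. Keep the paired tests on concentrations, including triglycerides.
2. Beside them, add the paired test of apo B/apo A1, and of total/HDL cholesterol if HDL is measured. The lipid and apolipoprotein section of Methods does not name HDL.
3. Where haemoglobin and haematocrit are available from the same draws, also report concentrations corrected for plasma-volume change, including the inflammation markers.
4. Attribute a concentration change to metabolism rather than fluid shift only when the ratio or the corrected values support it. Otherwise report it as a concentration change, with plasma-volume shift stated as a limitation.

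It would also help to state the interval between the last ride and the post-ride draw.

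The cost is wording and a few more comparisons; apo A1 and apo B are already measured. A ratio does not show a true parallel fall in all lipoproteins, and neither ratio contains triglycerides. That is why the concentrations should stay tested and not be replaced by ratios.

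### With 11 men, does using mean ± SD and a paired t-test for every marker, with no log scale or fallback, need changing?

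*Combined protocol and SAP*

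**What the plan says.** The Statistical Analyses section is three sentences long. The summary rule is "Data will be expressed as mean" ± SD. The main variables are "changes in visceral adipose tissue and ectopic fat as well as cardiometabolic risk markers". The test is given as "A paired t-test will be used with a significance level" of 0.05. No transformation, distribution check or rank-based alternative appears anywhere in the document.

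The sample is small: "A sample of eleven recreational middle-aged male cyclists" (Research Protocol). The markers include "fasting plasma lipoprotein-lipid profile and inflammation markers, glycated hemoglobin" (Research Protocol), and the plasma section of Methods adds that "Cholesterol and triglyceride levels are determined in plasma using automated techniques". For liver fat, Methods says "Proton Magnetic Resonance Spectroscopy (MRS) will be performed to determine liver fat content". On expected levels, the Research Protocol says "From their age, we expect them to have subclinical levels of visceral adipose tissue/ectopic fat". Baseline evaluations are repeated after the ride, with exceptions that do not touch the blood markers or fat depots, so pre/post pairs exist for all of these.

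The document gives no distribution, SD, effect size or power figure for any marker. The two hypotheses in the Background concern body composition, visceral and ectopic fat, and waist circumference. Neither predicts a fall in triglycerides or in an inflammation marker.

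**The concern.** A skewed baseline does not by itself harm a paired t-test, because only the differences enter it. Harm arises if change is also proportional to baseline. Men with high values then contribute larger absolute changes, the SD of the difference grows, and the test loses power.

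With 11 pairs there is little power to spare: 80% power needs a mean change of about 0.94 SD of the differences. A real percentage fall in triglycerides or an inflammation marker might therefore be reported as non-significant. A second worry is that silence about scale lets it be chosen once the data are known. A third is that mean ± SD describes the typical man poorly when a marker is skewed.

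**Working it through.** **Inputs.** From the documents: n = 11 pairs, paired t-test, level 0.05. Two-sidedness is assumed, giving a critical t on 10 df of 2.228. Everything else is an assumption: a log-normal baseline with log-SD s_b; a log ratio post/pre that is normal with mean ln(1 − fall) and SD s_w. The plan has no power figure to reproduce. Simulated powers use 40,000 trials per cell (standard error at most 0.25 points).

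**1. Proportional change, no additive reading error.** The noncentrality of the log-ratio test is −ln(1 − fall)/s_w × √11.
- 20% fall, s_w 0.25: 0.223/0.25 × 3.317 = 2.96, power 76%.
- 30% fall, s_w 0.35: 0.357/0.35 × 3.317 = 3.38, power 86%.

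| Baseline log-SD | Raw, 20% fall | Log | Raw, 30% fall | Log |
|---|---|---|---|---|
| 0.3 | 66% | 76% | 75% | 86% |
| 0.5 | 62% | 76% | 71% | 86% |
| 0.6 | 58% | 76% | 68% | 86% |
| 0.8 | 49% | 76% | 59% | 86% |
| 1.0 | 41% | 76% | 49% | 86% |

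For the 20% fall the raw test gives up 76 − 66 = 10 to 76 − 58 = 18 points at log-SD 0.3-0.6. If the same variability is split between the two readings, raw power at 0.3 / 0.5 / 0.6 is 72 / 66 / 61%, a loss of 4 to 15 points. The two lowest rows need extreme spread: the 95% range of a log-normal is exp(2 × 1.96 × s_b)-fold, which is about 3.2-fold at 0.3 and 50-fold at 1.0. Nothing in the protocol points to a 50-fold range in relatively fit, asymptomatic men.

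**2. Validity.** With no change in the log ratio (s_w 0.25), the raw test rejects in 2.8-4.8% of trials. It is conservative under strong skew and is not inflated.

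**3. Additive change.** Take a median of 1.2, mean change −0.24 and SD of change 0.27. The raw noncentrality is 0.24/0.27 × 3.317 = 2.95. Simulated raw power is 75-76%. Log power at log-SD 0.3 / 0.5 / 0.6 is 71 / 65 / 62%. The log scale now loses about 5 to 13 points.

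**4. Additive reading error on both readings** (20% fall, s_w 0.25, log-SD 0.3 / 0.5 / 0.6).
- Error SD 10% of the median: raw 53 / 50 / 48%, log 58 / 54 / 52%. The log gain is 4-5 points.
- Error SD 15% of the median: raw 43 / 40 / 39%, log 43 / 39 / 37%. The gain is nil or negative.

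**5. Scale chosen after the fact.** Counting a trial as positive if either scale gives P < 0.05, with no true change in the log ratio, the rejection rate is 5.7-6.3% at log-SD 0.3-1.0, against a nominal 5%.

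**6. Would a rank fallback help?** For a 20% fall with s_w 0.3, raw t against exact signed-rank is 49 against 46% at log-SD 0.3 and 45 against 45% at 0.5. The fallback gains only at strong skew (36 against 44% at 0.8).

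**7. Liver fat.** With an assumed median of 1.5%, log-SD 0.6, a 20% fall, and readings below 0.5 set to 0.25 for the log analysis, additive error SDs of 0 / 0.1 / 0.2 points give raw 58 / 53 / 42% and log 71 / 59 / 40%. The log advantage is gone by 0.2 points, and the protocol itself expects low levels. There is no case for moving liver fat off the stated test.

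**The case for a change.** The best argument for a change is that scale matters in a sample this small, whichever model is true. At baseline log-SD 0.3-0.6 the raw and log tests disagree on significance in 11-20% of trials under proportional change and in 12-19% under additive change. Naming a scale for triglycerides and inflammation markers would take two sentences, and under proportional change it would recover real power.

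The disagreement rate stands, but it does not say which scale to prefer. Within the same range of skew, the possible gain (10-18 points, or 4-15 with variability split between readings) is matched by a possible loss of 5-13 points, and the documents offer nothing to decide between them. The argument about freedom of choice is also limited. The section can fairly be read as fixing the raw scale, in which case a switch would be a visible departure. If it is read as leaving the scale open, the power loss is not a consequence of the plan, and the inflation is about one percentage point per marker.

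Making the log ratio primary for every inflammation marker has its own difficulty. The document does not name these markers or describe their assays, and readings near an assay limit would need the same kind of rule as liver fat near zero. The point about summaries stands in a small way: if a marker proves skewed, a median and quartiles belong beside the mean, which is ordinary reporting practice.

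**Conclusion.** No change follows. Carried out as written, the plan gives a valid test of mean change. It may be less powerful than a log-ratio test for triglycerides or an inflammation marker, by 10-18 points for a 20% fall at baseline log-SD 0.3-0.6. That figure rests on three assumptions found nowhere in the document: right skew, change proportional to baseline, and negligible additive reading error. With additive change the stated test is the stronger by about 5-13 points. With additive error of 10-15% of the median, the two are within about 5 points of each other. The cost of leaving the scale open is a rejection rate of about 6% instead of 5% per marker.

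This is a fair trade-off plus a gap that analysts fill sensibly. They may report a log ratio for triglycerides, with median and quartiles, as a supporting analysis beside the paired t-test. For visceral and ectopic fat, including liver fat, the check gives no reason to depart from the stated test.
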